9.2 Study device

Table 2 describes specific medical or surgical procedures involved in the use of the study device(s).

Table 2: Description of the exposure to the study device

Component	Medical or Surgical procedure		
	Implant	Retrieval	Non-invasive follow-up
18F Introducer kit	✓	✓	
LCP	✓	✓	✓
Delivery catheter	✓		
Retrieval catheter	✓ (possible but unlikely)	✓	
Nanostim Link			
Programmer and accessories	✓	✓	✓

9.2.1 List of other medical devices or medications to be used during the clinical investigation

During the implant procedure, the physician will place a small introducer sheath in the femoral vein and inject a small amount of contrast, typically less than 10cc, to opacify and characterize the femoral access site. Likewise, the physician will place a diagnostic pigtail catheter and inject a small amount of contrast, typically less than 10cc, to opacify and characterize the right ventricular anatomy prior to LCP implantation.

9.2.2 Number of study devices to be used

Sponsor anticipates that each subject will be implanted with one LCP device in the right ventricle. In circumstances where multiple devices enter the sterile field during an implant procedure, Investigator will record and report the number of devices attempted, the reason why they were not implanted, and the final outcome.

9.3 Study population

The inclusion and exclusion criteria are consistent with recommendations of the European Society of Cardiology,⁶ American College of Cardiology, American Heart Association, and the Heart Rhythm Society.⁷ Additionally, Sponsor has included Investigator input.

Eligibility for implant is based on conformance to all prospectively defined inclusion and exclusion criteria:

9.3.1 Inclusion criteria

Only subjects meeting all inclusion criteria (from 1 to 7) are eligible for study participation.

1. Subject must have one of the following clinical indications:
 - Chronic atrial fibrillation¹ with 2 or 3° AV or BBB block²; or
 - Normal sinus rhythm with 2 or 3° AV or BBB block and a low level of physical activity or short expected lifespan (but at least one year); or
 - Sinus bradycardia with infrequent pauses or unexplained syncope with EP findings.
2. Subject ≥ 18 years of age;
3. Subject has life expectancy of at least one year and is a suitable candidate based on overall health and well-being;
4. Subject is not enrolled in another clinical investigation with a treatment arm or that could confound the results of this study;
5. Subject is willing to comply with clinical investigation procedures and agrees to return for all required follow-up visits, tests, and exams;
6. Subject has been informed of the nature of the study, agrees to its provisions and has provided written informed consent, approved by the EC;
7. Subject is not pregnant and does not plan on getting pregnant during the course of the study.

¹ For purposes of this protocol, the term “chronic atrial fibrillation” is also defined as permanent atrial fibrillation.

² For purposes of this protocol, “chronic atrial fibrillation with 2 or 3° AV or BBB block” includes slow ventricular rates (with or without medication) associated with atrial fibrillation.

9.3.2 Exclusion criteria

Only subjects meeting no exclusion criterion (from 1 to 9) are eligible for study participation.

1. Known pacemaker syndrome, have retrograde VA conduction or suffer a drop in arterial blood pressure with the onset of ventricular pacing;
2. Hypersensitivity to < 1 mg of dexamethasone sodium phosphate;
3. Mechanical tricuspid valve prosthesis;
4. Pre-existing ventricular pacing or defibrillation leads;
5. Current implantation of either conventional or subcutaneous implantable cardioverter defibrillator or cardiac resynchronization therapy;
6. Presence of implanted vena cava filter;
7. Evidence of thrombosis in one of the veins used for access during the procedure;
8. Cardiovascular or peripheral vascular surgery/intervention within 30 days of enrolment;¹
9. Presence of implanted leadless cardiac pacemaker (NOTE: This criterion is applicable only for subjects undergoing an implant.)

¹ Recent cardiovascular or peripheral vascular surgery within 30 days of enrollment is defined as the following:

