3 STUDY SYNOPSIS

Title	Nanostim study for a leadless cardiac pacemaker system – the LEADLESS observational study
Study Device	Leadless cardiac pacemaker (LCP) system
Regulatory Classification of the Study Device	Active Implantable Medical Device (AIMD) 90/385/EEC.
Study Objective	
To confirm clinical performance and safety of the Nanostim leadless cardiac pacemaker system, within its intended use and according to its instructions for use, by confirming the acceptability of identified risks and detecting emerging risks on the basis of factual evidence.
 
A sub-set of patients enrolled in this study will be used to meet the Post Market Clinical Follow-Up (PMCF) requirement for CE mark. Once this sub-set of patients is enrolled and followed for 6 months, a report will be submitted indicating completion of this requirement.

Number of Institutions	Up to 100 study sites. 
Number of Subjects	A total of 1000 patients will be enrolled. The PMCF will be complete when data from 300 patients followed for 6 months are obtained.
Study Population	Subjects who are at least 18 years old, and who are indicated for a VVI(R) pacemaker Subjects who participated in the pre-CE mark LEADLESS study, in the Nanostim Delivery Catheter pre-CE mark study or were implanted with a Nanostim Leadless Cardiac Pacemaker within 3 months of the study start at one of the selected sites involving physician trainers and study leaders can be enrolled in this study. 

The LEADLESS Observational Study

Schedule of Assessments	
Enrollment, Implant, Pre-discharge, 90-day, 6-month and every 6-month follow-ups thereafter (until the last enrolled subject has completed a 5-year follow-up visit).
 
The PMCF requirement will be met when the 300th patient has completed the 6 month follow-up visit.

Study Design	Prospective, non-randomized, single-arm, multicenter, post-market study
Primary Endpoint	The primary safety endpoint is to evaluate a 180-day complication-free rate, where a complication is defined as a serious adverse device effect (SADE).
Additional Data	
- Pacing and sensing performance- All adverse events- Implant success rate- Procedure time- Time to discharge

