Schedule of Assessments	
a. For subjects with de novo Nanostim LCP implant or already implanted with a Nanostim LCP within 3 months of the study start at one of the selected sites
 
Enrollment Assessments
 
 • Inclusion/exclusion criteria • Informed consent • Medical history 
Implant Assessments
 
 • Femoral vein assessment and access • LCP implant • LCP assessment and programming • Assess for adverse events and device deficiencies 
Pre-Discharge Visit
 
 • LCP assessment and programming • Assess for adverse events and device deficiencies 
90-day Visit
 
 • LCP assessment and programming • Assess for adverse events and device deficiencies 
6-month Visit
 
 • LCP assessment and programming • Assess for adverse events and device deficiencies 
Every 6-month follow-up visits thereafter (until the last enrolled subject has completed a 5-year follow-up visit)
 
 • LCP assessment and programming • Assess for adverse events and device deficiencies 
Optional and only for subjects with de novo Nanostim LCP implant or already implanted with a Nanostim LCP within 3 months of the study start at one of the selected sites : 24-hour Holter Recording (involving approximately 25 subjects in the study, any time after first 30 days of follow-up)
 
b. For subjects who participated in the pre-CE mark LEADLESS study
 
Enrollment Assessments
 
 • Inclusion/exclusion criteria • Informed consent • Medical history • Assess for adverse events and device deficiencies 
90-day Visit (if visit occurred within 60-120 days post-implant)

- LCP assessment and programming
- Assess for adverse events and device deficiencies

6-month Visit (if visit occurred within 5-7 months post-implant)

- LCP assessment and programming
- Assess for adverse events and device deficiencies

Every 6-month follow-up visits thereafter (until the last enrolled subject has completed a 5-year follow-up visit)

- LCP assessment and programming
- Assess for adverse events and device deficiencies

The LEADLESS Observational Study

Table 1: Study flow and CRFs

CRFs	Pre-procedure	Procedure	Post-procedure Assessments			Additional Assessments	

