9.3.4 Recruitment and enrollment

Candidates for this clinical study include subjects indicated for a VVI(R) pacemaker. Pre-enrollment records will include evidence of diagnosis indicating need for VVI(R) pacemaker. Preoperative screening to confirm the diagnosis is not considered part of the clinical study; however, the informed consent form will inform the subject that their medical history records used to confirm diagnosis will be incorporated into the study record.

Enrollment begins when the subject provides written informed consent and agrees to participate in the clinical study. A total of 300 subjects are needed to meet the 6-month follow-up sample size. Additional subjects will be enrolled until approximately total 1000 subjects are enrolled and everyone will be followed for at least up to 5 years post implant to document the long term performance of the system.

Patients who participated in the pre-CE mark LEADLESS study, the Nanostim Delivery Catheter pre-CE mark study or were implanted with a Nanostim Leadless Cardiac Pacemaker within 3 months of the study start at one of the selected sites involving physician trainers and study leaders can be enrolled.

For the pre-CE mark LEADLESS study subjects, the data collection will start after consent is obtained and will include any study related adverse event documentation after the subject exited the pre-CE mark LEADLESS study.

For the Nanostim Delivery Catheter pre-CE mark subjects, the data collection will start after consent is obtained.

For subjects who were implanted with a Nanostim Leadless Cardiac Pacemaker within 3 months of the study start at one of the selected sites involving physician trainers and study leaders, the data collection will start after consent is obtained and will include implantation procedure, pre-discharge visit and any study related events (Adverse Event, Device Deficiency, additional visit, etc.).

Additionally, 24-hour Holter data will be collected in approximately 25 subjects any time after the first 30 days of follow-up.

Sponsor anticipates that the clinical study will be completed within 6 years.

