16.8 List of foreseeable adverse events and anticipated adverse device effects

The table below provides a list (non-exhaustive) of potential adverse events, device related, procedure related and/or subject condition related.

-Next Page-

Table 3: List of foreseeable adverse events and anticipated adverse device effects

Air embolism	Interruption of desired pacemaker function due to electrical interference, either electromyogenic or electromagnetic
Angina pectoris	Keloid formation
Arterial puncture	Loss of normal device function due to battery failure or component malfunction
Bladder puncture	Muscle and nerve stimulation
Blunted or poor sensor response	Myocardial damage
Body rejection phenomena	Myocardial infarction
Bowel penetration	Myocardial irritability
Cardiac arrhythmias	Oversensing
Cardiac dissection	Pacemaker syndrome
Cardiac perforation	Palpitations
Cardiac tamponade	Pericardial effusion
Chronic nerve damage	Pericardial rub
Damage to vessels	Pericarditis
Device dislodgment	Phrenic nerve/diaphragm muscle stimulation
Dizziness	Premature battery depletion
	Programmer/software anomaly
Dyspnea	Pseudoaneurysm formation
Embolism	Psoas abscess
Endocarditis	
Excessive Bleeding	Septic arthritis
Exit block	Seroma
Failure to capture/loss of capture	Syncope
Femoral nerve injury with resulting paresthesias	Threshold elevation
Fluid accumulation	Thromboemboli
Hematoma formation, including retroperitoneal hematoma/hemorrhage	Thrombosis
High impedance	Undersensing
Inability to interrogate or program due to programmer or device malfunction	Valve damage
Induced ventricular ectopy or arrhythmias	Venous occlusion
Infection, local at access site, or system	Venous perforation
Insufficient cardiac output	Ventricular ectopy
Intermittent capture	Ventricular tachycardia

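### Already-implanted patients are screened at enrolment, after their implant, so some with early serious complications can be missed; if this group counts, the 180-day complication-free rate can be biased upward

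*Combined protocol and SAP*

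**What the plan says.** The Study Synopsis and section 9.3.4 admit three kinds of patient who already carry the LCP. They are participants in the pre-CE-mark LEADLESS study, participants in the pre-CE-mark delivery catheter study, and patients who "were implanted with a Nanostim Leadless Cardiac Pacemaker within 3 months of the study start at one of the selected sites involving physician trainers". Section 9.3.4 dates enrolment from written consent, which for these patients comes after the implant.

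In the Synopsis, one schedule of assessments covers both de novo implants and subjects "already implanted with a Nanostim LCP within 3 months of the study start at one of the selected sites". It lists the inclusion and exclusion criteria as an enrolment assessment, as does the separate schedule for the pre-CE LEADLESS group. Section 9.3.2 opens with "Only subjects meeting no exclusion criterion (from 1 to 9) are eligible for study participation" and relaxes a single item, exclusion 9: "Presence of implanted leadless cardiac pacemaker (NOTE: This criterion is applicable only for subjects undergoing an implant". Exclusion 8 counts its 30 days from enrolment.

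For the within-3-months group, section 9.3.4 says that "the data collection will start after consent is obtained and will include implantation procedure, pre-discharge visit and any study related events". For the pre-CE LEADLESS group it collects only events after the subject left that study.

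The endpoint is defined in the Synopsis: "The primary safety endpoint is to evaluate a 180-day complication-free rate, where a complication is defined as a serious adverse device effect (SADE". Section 9.1.4 removes from the primary calculation subjects who were not successfully implanted or who consented without an implant attempt. It does not mention already-implanted subjects. The PMCF requirement is met when 300 subjects have completed 6 months (section 9.3.3).

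**The concern.** Most of these criteria describe a patient who has yet to receive the device. Applied weeks or more after implant, some of them can describe what the implant led to. A patient whose LCP failed and was replaced by a lead-based system may meet exclusion 4 or 5. Thrombosis in an access vein may meet exclusion 7, and a recent vascular or cardiac repair may meet exclusion 8. A patient who died cannot consent. Several such courses are endpoint events or markers of them, because a SADE takes in death, surgical intervention and significant loss of device function (sections 16.2 and 16.4).

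If these subjects are counted from the day of implant, the rate rests partly on a group from which some patients with events were removed before they could be counted. Retrospective collection recovers early events only in those who pass screening and consent. No maximum time from implant to consent is stated. The error would run in one direction, in favour of the device, in the endpoint that carries the PMCF requirement. Section 6.1 says that this requirement uses a reduced non-inferiority margin.

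**Working it through.** **1. The plan's own figure.** The 300 cannot be reproduced, because the expected rate, margin, alpha, power and dropout in section 6.1 are blacked out. A one-sample normal formula gives about 301 for unrelated assumed inputs (94% against 90%, one-sided 5%, 80% power; or 95% against 90%, one-sided 2.5%, 90% power), so a match would prove nothing. The point does not depend on it.

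**2. When eligibility is judged.** Four features point to the time of enrolment:
- the Synopsis lists the criteria among the enrolment assessments for already-implanted subjects;
- section 9.3.2 attaches the exclusions to participation in the study, not only to the implant;
- exclusion 8 is dated from enrolment;
- exclusion 9 needed a waiver. Had the criteria meant status before the original implant, an LCP already in place would not have needed one.

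No sentence states a reference date for these subjects.

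**3. Whether they count.** The within-3-months group shares the de novo schedule, including implant, pre-discharge, 90-day and 6-month assessments, and its implant data are back-filled. Section 9.1.4 does not remove it. Nothing visible expressly includes it in the 180-day rate or the PMCF 300.

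**4. Size, if they count.** None of these inputs is in the documents; all are assumptions:
- r, the true 180-day SADE rate: 4-8%
- f, the fraction of patients with a SADE who are never enrolled because of it: 25-75%
- s, the cohort's share of the analysis set: 10-30%

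Of all cohort patients, a fraction rf is lost. Among the remaining 1 - rf, the events number r(1 - f). So

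observed rate = r(1 - f)/(1 - rf), and shift = s × (r - observed rate).

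| r | f | s | Observed rate in cohort | Shift in pooled rate (points) |
|---|---|---|---|---|
| 4% | 25% | 10% | 0.030/0.990 = 3.03% | 0.10 × 0.97 = 0.10 |
| 6% | 50% | 20% | 0.030/0.970 = 3.09% | 0.20 × 2.91 = 0.58 |
| 8% | 75% | 30% | 0.020/0.940 = 2.13% | 0.30 × 5.87 = 1.76 |

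Standard error at n=300 and r=6%: sqrt(0.06 × 0.94/300) = 1.37 points. The half-width of a 90% interval is 1.645 × 1.37 = 2.26 points.

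**5. Sensitivity.** With r=6% and f=50%, a cohort share of 5% gives 0.05 × 2.91 = 0.15 points. A wider grid (r 4-10%, f 25-100%, s 5-30%) runs from 0.05 to 3.0 points. If the criteria caused no loss (f=0), the shift from them would be zero; loss through death or refusal before consent would remain.

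**6. Effect on a test.** Assume a one-sided 5% test at n=300 with the true rate exactly on the null boundary. The chance of a false pass is then Φ(-1.645 + shift/SE). With standard errors of 1.13, 1.37 and 1.57 points for the three rows, this is about 6%, 11% and 30%. The actual test level and margin are not visible.

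**The case against.** The strongest reply is that bias needs a premise the visible text does not supply, namely that these subjects enter the 180-day analysis. Section 10.1 refers to section 6.1 for the primary objective, and 6.1 is largely blacked out. This stands, and the conclusion has to be conditional.

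Second, judgement at consent is inferred. Section 9.3 ties eligibility to the implant, exclusion 4 speaks of leads that pre-exist, and exclusion 7 of veins used in the procedure. A pre-implant reading of those two is natural. It is harder to square with exclusion 8 and the exclusion 9 waiver. What stands is that the wording is open and different sites could apply it differently.

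Third, a reader might infer that every patient with an early complication is screened out, so that the cohort is selected on absence of the endpoint. The documents do not support that. A conservatively managed effusion or a threshold rise matches no exclusion, and a subject re-implanted with another LCP stays in follow-up (section 9.4.3). Early events in within-3-months subjects who do enrol are collected.

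Fourth, overlap with the list of foreseeable events is not overlap with the endpoint. Exclusion 1 ("Known pacemaker syndrome, have retrograde VA conduction or suffer a drop in arterial blood pressure with the onset of ventricular pacing") matches the entry "Pacemaker syndrome" in the table of section 16.8, but that table is not limited to serious or device-related events. Removing such a patient need not remove a SADE.

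Finally, leaving the cohort out of the primary rate may seem excessive when a reference date is one sentence. But a reference date cannot recover patients who died or declined before consent.

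**Conclusion.** The point holds in conditional form. The plan enrols some patients after implant, lists their eligibility check as an enrolment assessment and waives only exclusion 9. It leaves open whether they count in the 180-day rate. Some early serious complications can therefore keep a patient out, and if the group counts, the complication-free rate can be biased upward.

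The direction follows from the mechanism, but the size cannot be derived. Under the assumed inputs it is about 0.1 to 1.8 percentage points. The middle case of 0.6 is below half of one standard error, and the upper end needs all three assumptions at their extremes. A reader might infer that the reported rate is inflated, or that the PMCF conclusion would change. Neither can be shown, since the cohort's size and its place in the analysis are not stated and the margin is not visible. The change is still worth making, because it is cheap and removes a possible one-directional error from a safety endpoint.

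**What to change.** In sections 9.3.1 and 9.3.2 and in the Synopsis, state that for already-implanted subjects the clinical eligibility criteria are judged from records on status before the LCP implant. Add that conditions arising afterwards are recorded as adverse events and not used as exclusions.

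In sections 9.1.2, 9.1.4 and 10.1, state that the primary 180-day rate and the PMCF 300 are based on subjects who consented before implant.

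Report the already-implanted subjects separately, with the number of LCP implants at the selected sites in the window and the reasons for non-enrolment, including death.

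The cost is protocol wording, a short screening log at the selected sites, and a slightly later 300th evaluable subject within the 1000 already planned.

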9.3.3 Study duration

The minimum length of the clinical study for each subject will be 5 years. The PMCF requirement will be met when 300 subjects have completed 6 months of follow-up. Subjects will be required to return for follow-up at 90 days (+/- 1 month), 6 months (+/- 1 month) and every 6 months thereafter (+/- 2 months) until the last enrolled subject has completed a 5-year follow-up visit.

9.3.4 Recruitment and enrollment

Candidates for this clinical study include subjects indicated for a VVI(R) pacemaker. Pre-enrollment records will include evidence of diagnosis indicating need for VVI(R) pacemaker. Preoperative screening to confirm the diagnosis is not considered part of the clinical study; however, the informed consent form will inform the subject that their medical history records used to confirm diagnosis will be incorporated into the study record.

Enrollment begins when the subject provides written informed consent and agrees to participate in the clinical study. A total of 300 subjects are needed to meet the 6-month follow-up sample size. Additional subjects will be enrolled until approximately total 1000 subjects are enrolled and everyone will be followed for at least up to 5 years post implant to document the long term performance of the system.

Patients who participated in the pre-CE mark LEADLESS study, the Nanostim Delivery Catheter pre-CE mark study or were implanted with a Nanostim Leadless Cardiac Pacemaker within 3 months of the study start at one of the selected sites involving physician trainers and study leaders can be enrolled.

For the pre-CE mark LEADLESS study subjects, the data collection will start after consent is obtained and will include any study related adverse event documentation after the subject exited the pre-CE mark LEADLESS study.

For the Nanostim Delivery Catheter pre-CE mark subjects, the data collection will start after consent is obtained.

For subjects who were implanted with a Nanostim Leadless Cardiac Pacemaker within 3 months of the study start at one of the selected sites involving physician trainers and study leaders, the data collection will start after consent is obtained and will include implantation procedure, pre-discharge visit and any study related events (Adverse Event, Device Deficiency, additional visit, etc.).

Additionally, 24-hour Holter data will be collected in approximately 25 subjects any time after the first 30 days of follow-up.

Sponsor anticipates that the clinical study will be completed within 6 years.

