6.3 Long-term safety data

The study will observe and report all adverse events and device deficiencies. For the PMCF requirement, all safety data obtained when the 300th patient has completed the 6 month follow-up visit will be reported. The supplementary endpoints of the study are complication free rate at 90 days and 5 years.

Long-term safety of the Nanostim™ LCP will be evaluated in terms of freedom from complications through 60 months of follow up.

The performance goal for the Nanostim™ LCP in this study is set to allow a small margin of 5% below that observed in the FOLLOWPACE study. This performance goal will ensure that the Nanostim™ LCP will not have an unacceptably high rate of long-term complications in comparison with transvenous pacemakers.

The hypothesis is stated as follows:

- H_0 : Freedom from complications through 5 years (1825 days) $\leq 75\%$
- H_a : Freedom from complications through 5 years (1825 days) $> 75\%$

The hypothesis will be tested at the 5% significance level (1-sided).

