9.4.1 Enrollment assessment

The Investigator will not start any study-specific procedures or alterations of subject care until the informed consent process has been completed and Investigator obtains a signed Informed Consent Form. To determine eligibility, some screening procedures may be necessary. If any of these tests do not fall within the Investigator's standard clinical practice, they will be required for subjects to be enrolled in the clinical study.

During this visit, investigation team will collect medical history data.

In addition:

- For subjects who were previously implanted with a Nanostim LCP at one of the selected sites involving physician trainers and study leaders, investigation team will collect implant procedure data, pre-discharge data and any study related events (Adverse Event, Device Deficiency, additional visit, etc.).
- For pre-CE mark LEADLESS study subjects, investigation team will collect any study related adverse events.

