Investigator will use medical judgment and provide institutional standard of care for post-pacemaker-implant monitoring.

During this visit, investigation team will:

- Assess for adverse events, device deficiencies and deviations to this observational study plan,
- Check pacing capture threshold, R-wave amplitude, pacing impedance, and battery voltage,
- Adjust programmable parameters of LCP, as needed

9.4.4 90-day follow-up visit (within 60-120 days post-implant)

This section may apply to subjects who were previously implanted with a Nanostim LCP if the visit is within the 90-day visit window (within 60-120 days post implant).

All subjects will return to the implant center at the investigation site for a 90-day follow-up visit. During this visit, investigation team will:

- Assess for adverse events, device deficiencies and deviations to this observational study plan,
- Check pacing capture threshold, R-wave amplitude, pacing impedance, and battery voltage, and
- Adjust programmable parameters of LCP, as needed, and

9.4.5 6-month follow-up visit (within 5-7 months post-implant)

This section may apply to subjects who were previously implanted with a Nanostim LCP if the visit occurred within the 6-month visit window (within 5-7 months post implant).

All subjects will return to the implant center at the investigation site for a 6-month follow-up visit. During this visit, investigation team will:

- Assess for adverse events, device deficiencies and deviations to this observational study plan,
- Check pacing capture threshold, R-wave amplitude, pacing impedance, and battery voltage, and
- Adjust programmable parameters of LCP, as needed.

9.4.6 Every 6-month follow-up visits thereafter (until the last enrolled subject has completed a 5 year visit)

All subjects will return to the implant center at the investigation site every 6 months for a follow-up visit after the 6-month follow-up visit until the last enrolled subject has completed a 5 year visit. During this visit, investigation team will:

- Assess for adverse events, device deficiencies and deviations to this observational study plan,
- Check pacing capture threshold, R-wave amplitude, pacing impedance, and battery voltage, and
- Adjust programmable parameters of LCP, as needed.

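### For two previously implanted cohorts, capture of complications is not stated to start at implant, and the supplementary 5-year test against 75% has no day 0 and no late-entry rule

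*Combined protocol and SAP*

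**What the plan says.** Section 9.3.4 sets three capture rules for subjects who enrol with the device already in place.

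- **Implanted within 3 months of study start at a selected site:** collection starts at consent but "will include implantation procedure, pre-discharge visit and any study related events".
- **Pre-CE LEADLESS study:** collection starts at consent and adds "any study related adverse event documentation after the subject exited the pre-CE mark LEADLESS study".
- **Delivery Catheter pre-CE study:** "For the Nanostim Delivery Catheter pre-CE mark subjects, the data collection will start after consent is obtained". No look-back is given.

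Section 9.4.1 is worded differently. Its first bullet collects implant, pre-discharge and event data "For subjects who were previously implanted with a Nanostim LCP at one of the selected sites involving physician trainers and study leaders", without the 3-month limit. Its second collects study-related adverse events for LEADLESS subjects and gives no start date.

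In the synopsis, schedule (a) covers de novo and within-3-months subjects. Schedule (b) covers LEADLESS subjects, with 90-day and 6-month visits conditional on the post-implant window. Delivery Catheter subjects are in neither.

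Follow-up is timed from implant: section 9.3.4 says "everyone will be followed for at least up to 5 years post implant", and the 90-day and 6-month windows in 9.4.4 and 9.4.5 are post-implant.

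Section 6.3 says long-term safety will be "evaluated in terms of freedom from complications through 60 months of follow up". It tests freedom from complications through 1825 days against 75%, one-sided at 5%. The table in section 10.1 lists only a confidence interval for this rate.

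**The concern.** SADEs from the procedure and the first weeks belong in a complication-free rate measured from implant. If a subject enters months after implant, earlier SADEs are not collected, and the subject is still counted from implant, an early failure is recorded as a success. The error runs only one way, towards the device.

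Starting the clock at consent instead avoids counting unobserved time, but it skips the peri-implant period. If risk is highest then, this also favours the device.

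The 5-year comparison with 75% is the one numerical pass/fail criterion legible in the public text, and its stated 5% error rate assumes complete ascertainment. The plan does not say which clock applies or how late entrants are handled.

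**Working it through.** **The plan's own figure.** The 75% goal cannot be reproduced. It is set 5% below an external rate that the plan does not print, and no power or assumed true rate is given for the 5-year test. As a baseline, an exact one-sample binomial test with N = 1000, null 75% and one-sided 5% passes at 773 or more event-free subjects, with actual alpha 4.9%.

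**Inputs.** From section 6.3: null 75% (so 25% with a SADE by year 5 at the null) and one-sided alpha 5%. From the synopsis: N = 1000. Assumed, because the documents do not give them:
- the two cohorts' combined share, s = 2%, 5% or 10%;
- start of capture between day 90 and day 540 after implant;
- 6.5% of subjects with a SADE by day 180, with 50-90% of those in week 1 and the rest even to day 180;
- the remaining 25% - 6.5% = 18.5% spread evenly from day 180 to day 1825 (1645 days).

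**Share of 5-year SADEs before capture, g.**
- Day 90, 50% in week 1: 6.5 × (0.5 + 0.5 × 83/173) / 25 = 0.19. With 90% in week 1 it is 0.25.
- Day 180: 6.5 / 25 = 0.26.
- Day 365: (6.5 + 18.5 × 185/1645) / 25 = 0.34.
- Day 540: (6.5 + 18.5 × 360/1645) / 25 = 0.42.

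**Bias and false pass, if counted from implant with earlier SADEs unrecorded.** Bias = s × g × 25 points. SE = sqrt(0.75 × 0.25 / 1000) = 1.37 points. False pass = P(Z > 1.645 - bias/SE).

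| Share s | Bias, g = 0.19 | False pass | Bias, g = 0.42 | False pass |
|---|---|---|---|---|
| 2% | 0.10 points | 5.8% | 0.21 points | 6.8% |
| 5% | 0.24 points | 7.1% | 0.53 points | 10.4% |
| 10% | 0.48 points | 9.8% | 1.05 points | 19.1% |

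Worked cell: s = 10%, g = 0.42 gives 0.10 × 0.422 × 25 = 1.05 points; 1.05 / 1.37 = 0.77; P(Z > 0.875) = 19.1%. In counts, that is 1000 × 0.10 × 0.25 × 0.422, or about 10.5 subjects with an unseen SADE. For capture by day 365 (g = 0.34) the figures are 6.4%, 9.1% and 15.4%.

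**Cross-check.** A separate exact binomial mixture, assuming 3-10% of late entrants had an unrecorded SADE before entry, gives a false-pass rate of 6.1-9.8% at a 5% share and 7.5-17.7% at 10%.

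**Does a late-entry rule repair it?** Kaplan-Meier was simulated with 4000 runs, N = 1000, true rate 75%, entry at day 180 by event-free subjects only, and no dropout. Counting from implant at a 10% share, the test passes in 9.0% of runs (5% pre-entry risk) or 10.9% (7%). With a delayed-entry risk set it passes in 4.7-5.1% across shares of 3%, 10% and 20%, and the mean estimate is 75.0%.

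**The case against.** The best case against has four parts.

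**Other text may fill the gap.** The first bullet of section 9.4.1 may take in some Delivery Catheter subjects. Its second bullet has no prior-study-exit limit for LEADLESS subjects, and the conditional visits in schedule (b) can be read as using earlier visits. Medical history is collected at enrollment, and an adverse event form is available then. This softens the gap, most of all for LEADLESS subjects, who were under observation in their earlier study, so that their problem may be one of data linkage. But none of it states complete SADE capture from implant, and 9.3.4 reads more narrowly.

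**No text counts these subjects from implant.** A reader might infer that the plan does so. It does not say so: section 6.3 names no day 0. What stands is that nothing visible prevents it, and that the visit clock runs from implant.

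**The 5-year rate is supplementary.** No visible decision depends on passing it, and section 10.1 lists only an interval. That limits the consequence, but section 6.3 still states a hypothesis and an error rate.

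**The effect may be small.** This is so if few such subjects enrol. Much larger false-pass rates can be produced by placing half or more of all 5-year SADEs before capture. With 6.5% by day 180 and 25% by year 5, that share does not exceed 0.42 even for capture at day 540.

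**Conclusion.** The point holds for the supplementary 5-year test. Only the within-3-months cohort has a stated look-back to implant; sections 9.3.4 and 9.4.1 and the synopsis schedule do not agree; and section 6.3 gives neither a day 0 nor a rule for late capture. Any resulting error favours the device.

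The size is illustrative, because cohort shares, entry times and early SADE rates are not in the documents. Under the assumptions above, the false-pass rate is about 6-7%, 7-10% and 10-19% at shares of 2%, 5% and 10%. It is smaller if LEADLESS events are available from the earlier study. The table does not size the effect of a clock started at consent.

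A reader might extend this to the 180-day primary endpoint or the 300-subject PMCF set. The documents do not support that: the detail of section 6.1 is blacked out and may contain the relevant analysis-set rule. This should be fixed, but it does not call the study as a whole into question.

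**What to change.** 1. **Sections 9.3.4 and 9.4.1 and the synopsis schedule:** collect or import all SADEs since implant for the Delivery Catheter and LEADLESS cohorts, as is already done for the within-3-months cohort. State whether the first bullet of 9.4.1 covers Delivery Catheter subjects, and place them in a schedule.
2. **Sections 6.3 and 10.1:** name implant as day 0 for the 5-year rate.
3. **Where SADEs since implant cannot be obtained:** enter those subjects by left-truncated Kaplan-Meier from the start of capture (consent, or earlier-study exit for LEADLESS). Record prior-SADE status and keep anyone with an earlier SADE out of the risk set. If that status is unknown, leave the subject out of the 5-year test.
4. **Sensitivity analysis by entry route:** importing events does not repair selection, since subjects who died or lost the device before consent do not enrol.
5. **Section 6.1:** no change to the 180-day or PMCF analysis set is proposed. The sponsor should only check that the unredacted text treats these cohorts consistently.

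The cost is one data item or data link for two cohorts and a few sentences. If 5% of 1000 were left out of the 5-year test, the standard error would rise from 1.37 to sqrt(0.75 × 0.25 / 950) = 1.40 points; at 10% left out (n = 900) it would be 1.44.
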